8.5.2.4 Responder Analysis

Eye Level – Eye Responder

LogMAR BCVA

Eye Responder analyses will be carried out at the visit of interest for the following definitions:

- Eyes with an improvement of at least 15 ETDRS letters (equivalent to a decrease of at least 0.3 LogMAR) compared to baseline, or having a Snellen acuity equivalent better than 20/200.
- Eyes that lost less than 15 ETDRS letters (equivalent to an increase of less than 0.3 LogMAR) compared to baseline.
- For eyes with on-chart BCVA at baseline, an improvement of at least 15 ETDRS letters (equivalent to a decrease of at least 0.3 LogMAR) compared to baseline.

Number and percentage of responders and non-responders will be summarized at all the follow-up visits (Years 2, 2.5, 3, 4 and 5). A GEE model will be used for comparisons of all-GS010 eyes against all-sham eyes to each of the follow-up visits.

The analysis will also be performed to compare best-GS010 eyes against best-Sham eyes and worst-GS010 eyes against worst-Sham eyes, giving number and percentage of responders and non-responders. However, instead of using a GEE model, a logistic regression will be used for these analyses, as the data are independent.

The following responders analyses will be performed on all eyes, all GS010 eyes and all sham eyes.

- Eyes with Clinically Relevant Recovery (CRR) from baseline at visit of interest, defined as:
 - For eyes on-chart at baseline, an improvement of at least -0.2 LogMAR from baseline at visit of interest,
 - For eyes off-chart at baseline, eyes which became on-chart ($\text{LogMAR} \leq 1.6$) at visit of interest.
- Eyes with Clinically Relevant Recovery (CRR) from Nadir at visit of interest, defined as:
 - For eyes on-chart at Nadir, an improvement of at least -0.2 LogMAR from Nadir at visit of interest,
 - For eyes off-chart at Nadir, eyes which became on-chart ($\text{LogMAR} \leq 1.6$) at visit of interest.
- Eyes with change from baseline of at least -0.3 LogMAR at visit of interest
- Eyes with change from nadir of at least -0.3 LogMAR at visit of interest
- Eyes with change from baseline of at least -0.2 LogMAR at visit of interest
- Eyes with change from nadir of at least -0.2 LogMAR at visit of interest
- Eyes with $\text{BCVA} < 1$ LogMAR at visit of interest
- Eyes with $\text{BCVA} \leq 1$ LogMAR at visit of interest
- Switch from baseline off-chart to on-chart ($\text{LogMAR} \leq 1.6$) at visit of interest
- Number/percentage of on-chart eyes at visit of interest

LogCS

The following responders analyses will be performed on all eyes, all GS010 eyes and all sham eyes.

- Eyes with an improvement of at least 0.3 LogCS compared to baseline.
- Eyes with an improvement of at least 0.3 LogCS compared to nadir LogCS.
- For eyes with on-chart LogCS at baseline, an improvement of at least 0.3 LogCS compared to baseline.

- Switch from baseline off-chart LogCS to on-chart at visit of interest

Subject Level – Subject Responder

At subject level, the best outcome observed in either eye will be considered.

LogMAR

Subject Responder analyses will be carried out at visit of interest for the following definitions:

- Subjects with CRR from baseline in at least one eye at visit of interest.
- Subjects with CRR from nadir in at least one eye at visit of interest.
- Subjects with an improvement of at least -0.3 logMAR compared to baseline in at least one eye at visit of interest.
- Subjects with an improvement of at least -0.3 LogMAR compared to nadir in at least one eye at visit of interest.
- Subjects with an improvement of at least -0.2 logMAR compared to baseline in at least one eye at visit of interest.
- Subjects with an improvement of at least -0.2 logMAR compared to nadir in at least one eye at visit of interest.
- Subject with LogMAR BCVA value $\leq +1.0$ LogMAR in at least one eye at visit of interest.
- Subject with LogMAR BCVA value $< +1.0$ LogMAR in at least one eye at visit of interest.
- For patients with both eyes off-chart at baseline, switch from baseline to on-chart (LogMAR ≤ 1.6) in at least one eye at visit of interest
- Number/percentage of on-chart patients (at least one eye on-chart) at visit of interest
- Clinically Relevant stabilization (CRS): Patient having a LogMAR < 1.0 at baseline in at least one eye that was maintained in this eye at the time point of interest (final BCVA)
- Clinically Relevant Benefit (CRB): Treatment benefit manifests as a clinically relevant stabilization (CRS) or a clinically relevant recovery (CRR) from nadir or both

For the subject responder endpoint, a randomization test will be performed for each of the follow-up visits (Years 2, 2.5, 3, 4 and 5):

- Response status of subjects whose ETDRS scores of the treated eye are at least 15 letters better than the sham eye or whose treated eye has a LogMAR acuity of at least 0.3 LogMAR better than the sham eye at each long-term follow-up visit.

LogCS

Subject Responder analyses will be carried out at visit of interest for the following definitions:

- Subjects with an improvement of at least 0.3 LogCS compared to baseline in at least one eye.
- Subjects with an improvement of at least 0.3 LogCS compared to nadir LogCS in at least one eye.
- For subjects with both eyes off-chart LogCS at baseline, switch from baseline to on-chart LogCS in at least one eye at visit of interest

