1. INTRODUCTION

Disease Review

Leber Hereditary Optic Neuropathy (LHON) is a rare, maternally inherited mitochondrial genetic disease, typically presenting as a non-syndromic optic neuropathy. Retinal ganglion cells (RGC), whose axons form the optic nerve, are the major cellular target affected by the resultant mitochondrial dysfunction. LHON was the first inherited human disease associated with point mutations in the mitochondrial DNA (mtDNA)¹ and it is considered the most common inherited genetic mitochondrial disorder.² LHON is a rare disease, and in Northern Europe, an estimated prevalence ranging from 1 in 30,000 to 1 in 50,000 has been reported.^{3,4,5}

The clinical hallmark of LHON is central vision loss.⁶ This is accompanied by dysfunction of color and contrast vision and central and cecocentral visual field defects and a final visual acuity of 20/200 or worse in 98% of eyes.^{7,8} A prospective natural history study⁹ reported LHON subjects with the G11778A *ND4* mutation. The primary outcome was the finding of no significant difference in the Early Treatment Diabetic Retinopathy Study (ETDRS) visual acuity at 12, 24, or 36 months of follow-up compared to baseline at study entry. This finding was for the entire cohort as well as for the subgroups of patients who entered the study within 12 months of disease onset or after 12 months of disease onset. Improvement by ≥ 15 ETDRS letters occurred in 14.7% of total study eyes in 18% of study patients over the study period. Eighty-six percent of patients had eyes with stable acuities during study follow-up. Subjects entering the study after 36 months from disease onset showed no change or improvement of visual acuity over follow-up. The authors concluded that for the G11778A *ND4* mutation spontaneous natural recovery is partial and occurs on a very limited basis in a small percentage of subjects, and thus, gene therapy interventions can be measured for efficacy with a reasonable sample size.

Long-term Follow-up of the Benefits and Risks of Study Treatment

Investigational Medicinal Product

This long-term follow-up study is non-interventional, hence no investigational medicinal product (IMP) will be administered. GS010 was administered to subjects via standard intravitreal (IVT) injection in RESCUE and REVERSE. Please see the Phase III study protocols or the Investigator's Brochure for details on the IMP.

Generation of GS010 Safety Profile

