5.4 DERIVED VARIABLES

ETDRS Score and LogMAR (on chart and off chart)

- ETDRS score is calculated by the examiner and written on the source documents and entered in the eCRF.
- LogMAR (on chart and off chart) will all be derived in eCRF from the Snellen/decimal acuity.
 - I. 1 ETDRS line = 5 letters
 - II. 1 ETDRS line = 0.1 LogMAR
 - III. 0.1 LogMAR = 5 ETDRS letters
 - IV. 15 ETDRS letters = 0.3 LogMAR
 - V. A less positive/more negative LogMAR is an improvement of vision
 - VI. An increase in the number of ETDRS letters read is an improvement of vision
- On-Chart subjects: defined as being able to read at least 3 ETDRS letters on a single line on the ETDRS chart at either 4 or 1 meters
 - a. Have an obtainable Snellen equivalent obtained directly from ETDRS chart

- b. Each Snellen equivalent is assigned a LogMAR value. A Snellen score of 6/6, 20/20, indicating that an observer can resolve details as small as 1 minute of visual angle, corresponds to a LogMAR of 0, since the base-10 logarithm of 1 is 0. A Snellen score of 6/12, 20/40, indicating an observer can resolve details as small as 2 minutes of visual angle, corresponds to a LogMAR of 0.3, since the base-10 logarithm of 2 is near-approximately 0.3, and so on.
- Off-chart subjects: defined as a subject who cannot read at least 3 ETDRS letters on a single line of the ETDRS chart at 1 meter and thus have no Snellen equivalent obtainable from ETDRS chart
 - a. These subjects are categorized as able to either count fingers (CF), detect hand motion (HM), detect light perception (LP), or are no-light perception (NLP).
 - b. If there is no CF and HM and a subject's visual acuity is light perception, then a LogMAR value of 4 will be assigned. If a subject's visual acuity is no light perception, then a LogMAR value of 4.5 will be assigned.
 - c. For those categorized as CF a LogMAR value of 2 will be assigned (Lange equivalence)
 - d. For those categorized as HM a LogMAR value of 2.3 will be assigned (Lange equivalence).

LogCS

Contrast sensitivity was assessed using the Pelli-Robson chart for low vision, on a scale from zero to 2.5 LogCS. Subjects who could not read at least 2 out of the first 3 letters on the Pelli-Robson chart will be assigned the worst possible score (a LogCS of zero).

- LogCS is obtained based on which letter triplets the subject can read correctly on the chart, and the LogCS value is then entered in the eCRF.

Nadir of LogCS

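### Subject-level Clinically Relevant Benefit is described as treatment benefit, yet the sham eye alone can satisfy it, and neither it nor its stabilization component is reported by GS010 and sham eye

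*SAP*

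**What the plan says.** The subject-level part of SAP 8.5.2.4 opens with a general rule: "At subject level, the best outcome observed in either eye will be considered". Three definitions in the list that follows matter here.

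- CRR from nadir needs only one qualifying eye.
- CRS needs a LogMAR below 1.0 "at baseline in at least one eye that was maintained in this eye at the time point of interest".
- CRB joins the two: "Clinically Relevant Benefit (CRB): Treatment benefit manifests as a clinically relevant stabilization (CRS) or a clinically relevant recovery (CRR) from nadir or both".

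None of the three is limited to the GS010 eye. SAP 3.1 states that each subject received GS010 in one eye and sham in the other.

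The eye-level part of the same section does separate the arms. It says "The following responders analyses will be performed on all eyes, all GS010 eyes and all sham eyes", and the list includes CRR from baseline, CRR from nadir and BCVA below 1 LogMAR. "Eyes that lost less than 15 ETDRS letters" is a further eye-level definition, compared between GS010 and sham eyes by GEE. CRS and CRB are not in the eye-level part, and no other section splits them by eye.

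One subject-level endpoint does contrast the two eyes: "For the subject responder endpoint, a randomization test will be performed for each of the follow-up visits". The single item under that sentence asks whether the treated eye is at least 15 letters or 0.3 LogMAR better than the sham eye.

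CRS and CRB do not appear among the endpoints in protocol 7.2.2 or SAP 4.3, nor in the list of changes in SAP 8.8.

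**The concern.** The definition attributes an outcome to treatment when either eye, including the untreated one, can produce it. Because all subjects were treated, the either-eye percentage has no untreated comparator. SAP 8 assigns logistic regression to subject responder endpoints, but for CRB there is no untreated group to put in the model. The SAP acknowledges the same limit for quality of life, which it presents for all subjects only.

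Followed as written, the plan yields a CRB percentage that mixes GS010-eye outcomes, sham-eye outcomes, natural recovery and plain stability. Without matching rates for GS010 and sham eyes, a reader cannot tell how much of it belongs to GS010.

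**Working it through.** The documents give no expected rate, sample size or power for CRS or CRB, so there is no figure to reproduce. The check is mainly of definitions. I read CRS as LogMAR below 1.0 at baseline and still below 1.0 in the same eye at the visit. SAP 5.4 equates 0.1 LogMAR with 5 letters.

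**1. Can the sham eye alone qualify a subject?** Take a GS010 eye going from 0.7 to 1.3, with 1.3 its worst reading. It loses 0.6 LogMAR, or 6 × 5 = 30 letters. It fails CRS, and its change from nadir is zero. The sham eye stays at 0.9, so it meets CRS. The subject meets CRB.

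**2. Can the planned eye-level rows stand in for CRS?**

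| Eye, baseline to visit | CRS | Lost less than 15 letters | BCVA < 1 at visit |
|---|---|---|---|
| 0.9 to 0.9 | yes | yes | yes |
| 1.5 to 0.9 | no | yes | yes |
| 0.2 to 0.9 (35 letters lost) | yes | no | yes |
| 1.3 to 1.3 | no | yes | no |

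The first two eyes agree on both planned rows and differ on CRS. An eye going from 1.0 to 0.9 without an intermediate dip is closer still. Like the stable 0.9 eye, it has no 0.2 or 0.3 gain and no CRR, and it is below 1 at the visit, but it is not CRS. So the planned rows do not determine CRS. CRB is a union of CRS and CRR from nadir, so it also needs their overlap, which separate totals do not give.

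**3. What does anchoring to nadir do?** SAP 5.4 defines nadir as the worst value up to and including the visit, with baseline included, so nadir is never better than baseline. Taking on-chart as LogMAR 1.6 or better, every eye with CRR from baseline therefore also has CRR from nadir. The reverse is not true: an eye going 0.5, 1.2, 1.0 gains 0.2 from nadir and qualifies, yet is 0.5 LogMAR (25 letters) worse than baseline. Measurement noise in on-chart eyes pushes in the same direction. Stable off-chart eyes are unaffected because their values are fixed: "For those categorized as CF a LogMAR value of 2 will be assigned".

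**4. Illustration from the documents' own figures.** SAP 1 reports, for a natural-history cohort, a gain of at least 15 letters in "14.7% of total study eyes in 18% of study patients over the study period". Assume that each patient contributed two exchangeable eyes.

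- Both eyes gained: 2 × 14.7 − 18 = 11.4% of patients.
- One given eye only: 14.7 − 11.4 = 3.3%.
- Total: 11.4 + 3.3 + 3.3 = 18%.
- Share of either-eye responders qualifying through one given eye alone: 3.3 / 18 = 18%.
- Share in whom that given eye responded at all: 14.7 / 18 = 82%.

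This is a 15-letter endpoint from baseline, not CRB.

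**5. Upper bound.** With exchangeable eyes and no treatment effect, sham-only and GS010-only cases are equally frequent. Sham-only cases then cannot exceed half of all CRB cases.

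**The case against.** The case for leaving the text alone has weight. Safety is the primary objective, SAP 8.5.1 names no primary efficacy variable, SAP 8.5.4 makes all efficacy analyses secondary without multiplicity adjustment, and no hypothesis attaches to CRB. The either-eye rule is stated openly. The endpoint's name is Clinically Relevant Benefit, the words about treatment are explanatory, and nothing says that a table will carry them. Most of the contrast between the arms is already planned, including CRR from nadir beside CRR from baseline. All of this stands, and it makes the point minor. It does not supply the missing CRS and CRB rates by arm, nor does it justify a causal word for an uncontrolled rate.

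It might also be argued that GS010 helps the fellow eye. The documents offer no such rationale, and the either-eye rate could not separate that effect from natural recovery.

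Three stronger readings are tempting but unsupported.

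- A reader might infer that the responder analyses lack a sham control. They do not; the gap is CRS and the composite.
- A reader might infer that CRB inflates the error rate of an efficacy claim. No test or decision rule for CRB is specified.
- A reader might want a predicted false CRB rate. Simulations with no true change gave either-eye rates from 0.4% to 39%. The inputs were all assumed: measurement SD 0.05 or 0.10 LogMAR, 50% or 80% of subjects off-chart in both eyes, 0 to 20% with one eye below 1.0, 6 or 14 readings, and between-eye noise correlation of 0 to 0.8. The sham-only share, capped at 50%, was about 38–50% at SD 0.05 and 22–43% at SD 0.10. Such figures mostly return their inputs and are not estimates for this study.

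**Conclusion.** The point holds as a minor one. On the text alone, a subject whose only qualifying eye is the sham eye is counted as showing treatment benefit, and neither CRS nor CRB has matching GS010-eye and sham-eye rates. This rests on no numerical assumption.

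The size in this study cannot be derived from the documents. The natural-history figures show only that an either-eye rate can be substantial without this treatment (18% for a 15-letter gain). The 18% share attributable to one given eye alone also needs the two-exchangeable-eyes assumption. What is affected is the interpretation of one secondary rate, not a primary conclusion.

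**What to change.** 1. In SAP 8.5.2.4, replace the treatment wording with a neutral definition, such as: subject with CRS, CRR from nadir, or both, in either eye; a descriptive outcome without an untreated comparison.
2. Report CRS (denominator: eyes with baseline LogMAR below 1.0) and CRB for GS010 eyes and for sham eyes. Split the CRB subjects into those qualifying by the GS010 eye only, the sham eye only, or both. Use the GEE that SAP 8 already assigns to eye responders where there are enough eyes, with the minimum stated in advance, and counts only otherwise.
3. Show the baseline-anchored composite (CRS or CRR from baseline) beside CRB.

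The cost is a wording change and a few table rows from data already collected. A per-eye CRB is a new derived variable and should be listed in SAP 8.8. CRS within RESCUE or REVERSE alone may rest on few eyes, and cells of non-responders may be empty because stable eyes below 1.0 nearly all meet it. The benefit claim becomes less prominent. The either-eye percentage itself does not change.

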8.5.2.5 Humphrey Visual Field Parameters

Mean deviation (MD) in decibels of sensitivity and foveal threshold sensitivities will be summarized by all eyes, all-GS010 eyes and all-sham eyes; along with change from baseline to each follow-up visit, using summary statistics for continuous variables.

The changes from baseline to 5 years of each data point of HVF, with the following thresholds of gain or loss: ≥ 7 dB; 5-6.99 dB; 3-4.99 dB; ≤ 2.99 dB, will be provided. Data of each individual patient (2 HVFs results per patient) will be described.

8.5.2.6 Goldmann Applanation Tonometry

Intraocular pressure (IOP) measurement (mmHg) in each follow-up visit and change from baseline to follow-up visits (Years 2, 2.5, 3, 4, and 5) will be summarized by all-GS010 eyes and all-sham eyes using summary statistics for continuous variables. Ocular and Slit-Lamp Examination

The result (normal/abnormal) before pupil dilation and after dilation for baseline and all follow-up visits (Years 2, 2.5, 3, 4, and 5) will be summarized by all-GS010 eyes and all-sham eyes and anatomical location using counts and percentages.

Quality-of-Life Analyses

Total scores and change of VFQ-25 and SF-36 scores (all individual domains and subdomains) from baseline to each follow-up Visit (Years 2, 3, 4, and 5) for all subjects will be assessed and summarized descriptively. Note that results will be presented in all subjects only, as all subjects are treated with GS010.

8.5.3 Methods for Handling Dropouts and Missing Data

Methods for dealing with missing data are detailed in [Section 5.5](#).

8.5.4 Multiplicity

The primary objective of this study is to assess the long-term safety of intravitreal GS010 administration up to 5 years post-treatment in subjects who were treated in the RESCUE or REVERSE studies. All efficacy analysis will be secondary analysis. No adjustment of multiplicity will be applied.

8.6 SAFETY ANALYSES

All safety analysis will be conducted on the Safety Population and summarized by treatment actually received.

8.6.1 Adverse Events

All adverse events analyses will be presented with number of patients with at least one AE and number of events.

Primary Safety Analysis

The primary safety variables are:

- Adverse events (AEs) or serious adverse events (SAEs) (ocular or systemic) related to IMP (=GS010=study drug) or administration procedure, as judged by the Investigator, reported during the long-term follow-up visits (2, 2.5, 3, 4, and 5 years) from the period of 96 weeks up to 5 years post-treatment and summarized descriptively by type, frequency (number, percentage), severity, causal relationship, and seriousness.

Adverse events and SAEs related to study drug or study procedure will be summarized in two different ways: (1) systemic AEs and SAEs related to study drug or procedure or both, and (2) ocular AEs and SAEs related to study drug or procedure or both. Systemic AE data will be summarized by all subjects. Ocular AE data will be summarized by sham eye only, GS010 eye only, and both eyes.

The following summaries will be produced for (1) SAEs unrelated to study drug or procedure or both, (2) systemic AEs/SAEs related to study drug or procedure or both, and (3) ocular AEs/SAEs related to study drug or procedure or both, using counts and percentage as follows:

- Overall summary of AEs/SAEs related to study drug or procedure or both
- AEs related to study drug or procedure or both, including the number of events reported
- AEs/SAEs related to study drug or procedure or both by maximum severity
- AEs/SAEs related to study drug or procedure or both leading to study discontinuation
- SAEs related to study drug or procedure or both
- SAEs related to study drug or procedure or both leading to death.

Note that AE summaries will be provided for AEs collected during the originating study (RESCUE or REVERSE studies), for the follow-up period of CLIN-06, and combined.

Events will be coded using the current version of MedDRA and summarized by system organ class (SOC) and preferred term (PT).

Secondary Safety Analysis

The secondary safety endpoints are:

- Ocular or vision-related adverse events reported during the post-treatment long-term follow-up visits from the period of 96 weeks up to 5 years and summarized descriptively by type, frequency (number, percentage), severity, causal relationship, and seriousness.

The number, type, frequency, and severity of ocular or vision-related AEs, including those with no relation or any relation to the study drug or procedure will be presented in the same way that the primary endpoint of ocular AEs/SAEs related to study drug or procedure.

Listings of AEs, SAEs, ocular AEs, and AEs leading to death will also be presented.

Events will be coded using the current version of MedDRA and summarized by system organ class (SOC) and preferred term (PT).

A summary of AEs leading to discontinuation will be provided, grouped by system organ class and preferred term. A further tabulation presenting the preferred terms for the events in descending order of frequency will also be presented. All AEs recorded on the eCRF will be listed.

